#### **10.0 Vulnerable Populations**

10.1 Vulnerable Populations:

VERSION DATE: 6/28/17

- $\boxtimes$  Children
- ⊠ Pregnant women/Fetuses/Neonates
- $\Box$  Prisoners
- □ Adults lacking capacity to consent and/or adults with diminished capacity to consent, including, but not limited to, those with acute medical conditions, psychiatric disorders, neurologic disorders, developmental disorders, and behavioral disorders
- $\boxtimes$  Non-English speakers
- $\boxtimes$  Those unable to read (illiterate)
- $\Box$  Employees of the researcher
- $\Box$  Students of the researcher
- $\Box$  None of the above
- 10.2 Additional Safeguards: This study is aimed at optimizing the nutrition provided to preterm born neonates. Given this and the potential benefit to them they will be included in the study. Consent will be obtained from parents (mom and/or dad (if married)). Non-English speakers and illiterate persons will be included in the study, but not targeted, to allow for diversity in the study and equal opportunity for participation and potential benefit.

#### **11.0** Local Number of Participants

11.1 Local Number of Participants to be Consented: We will plan to enroll approximately 80 infants in this study. We will potentially consent up to 100 infants, as some infants who are prenatally consented will no longer be eligible to participate in the study at the time of birth. For example, parents may give consent at 26 weeks gestation, but the infant may remain in utero until 33 weeks gestation, at which time they would no longer be eligible to participate.

#### **12.0 Local Recruitment Methods**

12.1 Recruitment Process: Admissions to the antepartum unit and to the NICU will be screened daily by the inpatient research coordinator for potential eligibility for the trial. Once identified, the coordinator will present the mother/parents with a study brochure and offer to share more information and answer questions regarding the study if the family is interested. When possible, and if there is IRB approval for this, consent will be obtained prior to delivery. If unable to obtain consent prior to the infant's delivery, the family will be approached within 12 hours of delivery to explain the study, answer questions and obtain consent. They will be allowed ample time to consider participation, as well as to ask questions of the clinical care team/PI regarding the study.

- 12.2 Source of Participants: The Epic (EMR) census for antepartum, labor and delivery and the NICU will be screened by the research coordinator.
- 12.3 Identification of Potential Participants: The unit census will be reviewed daily by the inpatient research coordinator to identify eligible patients. These patients will be drawn from the PI's patient population. Prior to birth, this will include mothers who have had a Neonatal Intensive Care Unit consult placed. After birth, parents whose infant is under the care of the PI and/or her colleagues will be approached. Patients will not selfidentify, but rather will be approached based on eligibility criteria that is contained in the medical record (i.e. gestational age). The inpatient study coordinator will present the parent(s) with a brochure describing the study. Following this initial contact, the study coordinator will follow-up with parents at their convenience to describe the study in more detail and answer any questions before obtaining consent. The family will also have an opportunity to meet with the PI or another neonatologist if requested to answer questions regarding the study. Those patients who have "research opt out" in their medical record will not be approached for participation in this study.
- 12.4 Recruitment Materials: Parents will initially be given a study brochure that generally describes the study. If the parents are then interested in hearing more about the study, they will be given a consent form and a time to discuss the details of the study with the inpatient study coordinator, their care teams and/or the PI.
- 11.5 Payment: \$25 Target gift cards will be given to each subject's parent at 3 time points (including discharge and the 2 outpatient visits).

### **13.0** Withdrawal of Participants

- 13.1 Withdrawal Circumstances: There are no specific circumstances under which the infant will be withdrawn from the study without parental consent; however changes in the nutrition protocol for the study can be made at the discretion of the attending neonatologist. These changes will not preclude continuing in the study, but rather will be adjusted for when analyzing the study data. On the other hand, parents can withdraw their infant from the study at any time point.
- 13.2 Withdrawal Procedures: If the infant is withdrawn from the study prior to study completion (4 months corrected age), the data collected prior to withdrawal will be analyzed, but no further data collected.
- 13.3 Termination Procedures: If the infant is withdrawn from the study, the remainder of their NICU care will be per standard NICU protocol. Again, data collected prior to withdrawal will be analyzed, but no further data collected.

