### 3.0 Study Outcomes

- 3.1 Primary Outcome: The primary outcome of this feasibility trial will be to determine if infants randomized to the enhanced nutrition protocol receive higher amounts of calories and protein throughout the first week of hospitalization.
- 3.2 Secondary Outcomes: The secondary outcomes will include measures of growth, neurodevelopment and growth hormone levels. Specifically, we will examine growth, not only in weight and length, but also in different compartments (FFM and FM) using weekly ADP measurements. We will also continue to track gains in these compartments beyond hospital discharge until 4 months CA. For neurodevelopment, we will utilize ERP techniques to look specifically at the effects of early enhanced nutrition on neural speed of processing and early cognition. Finally, we will look at the effect of early enhanced nutrition on IGF-1 and IGF-BP3 levels.

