Markers of Growth hormone axis activity (Outcomes for Aim 3): IGF-1 and IGFBP3 levels will be obtained in serum at 1 week of age and ~35 weeks CA. These specific markers were chosen as associations have been seen between linear growth, FFM gains, metabolic risk (e.g. increased adiposity and higher blood pressure), neurodevelopmental outcomes and IGF-1 and IGFBP3 in preterm born infants . IGF-1 and IGFBP3 will be analyzed by the Fairview Clinical Laboratory.

Additional Measures: The randomized design of this trial is expected to make the distribution of potential confounder values and characteristics similar in the intervention and control groups. Nonetheless, to confirm their equivalence and to describe the study sample, we will obtain birth anthropometrics, maternal age, education, and ethnicity, infant sex, gestational age at birth, weight-for-age z score at birth, and degree of illness from the medical record or parental self-report at enrollment. Degree of illness will be assessed using the Score for Neonatal Acute Physiology (SNAP) on DOL#1, 7, 14 and  $21^{34-35}$ . We will also collect data on other non-specific markers of illness, including days on the ventilator, requirement for blood pressure support, sepsis evaluations and antibiotic therapy, steroid administration, necrotizing enterocolitis (NEC), diagnosis of chronic lung disease and retinopathy of prematurity (ROP) etc. These measures will also allow us to track the safety of the intervention to ensure that rates of these common morbidities are similar in both groups.

5.3 Storage and Access: The records of this study will be kept private. In any publications or presentations, we will not include any information that will make it possible to identify the mother or baby as a subject. Any hard copies of the baby's research records will be kept in a locked desk in the locked office of the PI, co-I or study coordinator, and will be identified ONLY by an assigned study ID number (other identifying information will be removed). The study information will not be recorded in the medical record. These de-identified data will be entered into electronic format for storage and analysis; only the PI, co-Is, study coordinators and data analyst will have access to this electronic dataset.

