#### 16.0 Data Management

15.1 Data Analysis Plan: Data from the various domains will be entered by the study personnel into a web-based secure database (RedCap) for storage, retrieval and analysis. The NICU dietician is responsible for abstracting nutritional data from the electronic medical record (Epic). ADP data will be entered into the database by the study coordinators. ERP data will be abstracted by [name] and cleaned of artifacts as previously described. The data analyst will examine each variable for outliers and distributional properties and flag and correct entry errors where possible

and will log-transform or otherwise normalize variables prior to analysis. From RedCap all datasets will then be securely stored using Box.com per the HRPP policy. They may need to be downloaded to University/AHC desktops for statistical analysis, however only a subset of the team will be given access to all files (study coordinator and PI) and the rest will have access to the de-identified files only. These laptops are password protected and maintained by the AHC. Although we do not anticipate many missing values in this short-term follow-up study, multiple imputation methods (e.g., Proc MI in SAS) will be used if missing data can reasonably be considered missing at random. Analyses will also be run without imputation and results compared. Analyses will be carried out using SAS version 9.4 (SAS Institute Inc.) using an intent-to-treat approach, with a 2tailed p<0.05 as the threshold for statistical significance. For Specific Aims 1, 2, and 3, body composition data, neurodevelopmental outcomes, and IGF-1 and IGFBP3 will be treated as continuously-distributed variables assessed at multiple time points. For the ERP outcomes (which are measured twice), the primary hypotheses will be addressed using a simple general linear regression model for term-equivalent measures, and another similar model for 4 month corrected age measures, with assigned group as the independent variable in both cases. For FFM (with up to 10 repeated measures) and IGF-1 models, mixed effects regression models (using

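### Parental withdrawal ends all data collection, with no option to keep chart-based intake and safety data, which can modestly bias the intake comparison and under-count harm

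*Combined protocol and SAP*

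**What the plan says.** All references are to the combined protocol and SAP.

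- **Parental withdrawal.** Section 13.1 says that "parents can withdraw their infant from the study at any time point". Under 13.2, "the data collected prior to withdrawal will be analyzed, but no further data collected"; 13.3 says the same. Neither excepts chart data, safety events or vital status.
- **Care afterwards.** Section 13.3: "If the infant is withdrawn from the study, the remainder of their NICU care will be per standard NICU protocol". Clinical records therefore go on being made.
- **Changes by the attending.** Section 13.1 lets the attending neonatologist alter the study nutrition and adds: "These changes will not preclude continuing in the study".
- **Outcomes affected.** The primary outcome (3.1) is whether enhanced-arm infants "receive higher amounts of calories and protein throughout the first week of hospitalization". Morbidity data (5.2, Additional Measures) are meant to "track the safety of the intervention to ensure that rates of these common morbidities are similar in both groups".
- **Data source.** Under 16.0 Data Management, the items numbered 15.1 and 15.3 have intake and clinical outcomes abstracted from the electronic medical record.
- **Analysis.** Item 15.1 analyses "using an intent-to-treat approach", with multiple imputation if missing at random is reasonable and a comparison with unimputed results. It gives no analysis for data missing not at random and no rule for a partly observed first week.

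**The concern.** Two infants may leave the enhanced schedule on the same day. If the attending made the change, the infant is followed to 4 months corrected age. If a parent withdrew the infant from the study, the record ends that day. The protocol describes nothing in between, such as ending study nutrition or visits while permitting the chart to be read.

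For intake, labs and morbidities up to discharge, the loss comes from the rule and not from feasibility: the infant is normally still in the unit, the chart exists, and no contact with the family is needed. An intent-to-treat comparison needs outcomes on every randomised infant as far as they can be had. Section 14.1 asks whether enhanced provision will hold or be scaled back because of intolerance. A withdrawal prompted by intolerance bears on that question, and recording would stop just there. Later events in that infant would also be missing from the between-group morbidity comparison and from the single interim review by the safety committee (18.2).

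**Working it through.** **1. The plan's own figures (table in 4.1, kcal/kg).**
- Control: 26 + 40 + 55 + 70 + 75 + 80 + 85 = 431; 431/7 = 61.6 per day.
- Enhanced: 47.5 + 55 + 77.5 + 85 + 92.5 + 95 + 95 = 547.5; 547.5/7 = 78.2 per day.
- Planned difference: (547.5 − 431)/7 = 16.6 per day.

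Both printed totals reproduce. The only loss figure is about 12% after discharge (15.2), by which time first-week intake is already recorded. There is no in-hospital withdrawal rate.

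**2. One enhanced infant withdrawn after Day 3, then fed as the control row (assumed).**
- Recorded mean, Days 1–3: (47.5 + 55 + 77.5)/3 = 60.0.
- True week mean: (180 + 70 + 75 + 80 + 85)/7 = 490/7 = 70.0.
- Week mean if Days 4–7 are imputed from peers still on schedule: 547.5/7 = 78.2.
- Error for that infant: 60.0 − 70.0 = −10.0, or 78.2 − 70.0 = +8.2.

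**3. Effect on the arm difference, 4 of 40 enhanced infants and no controls (assumed).**
- True difference: (36 × 78.21 + 4 × 70.0)/40 − 61.57 = 15.82.
- Infants omitted, or imputed from peers: 78.21 − 61.57 = 16.64, an error of +0.82.
- Recorded days averaged: (36 × 78.21 + 4 × 60.0)/40 − 61.57 = 14.82, an error of −1.00.

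These are 5% and 6% of 16.64. The sign depends on a partial-week rule that the plan does not state.

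**4. Range.** With 1 to 5 such withdrawals after Day 1 to Day 5, omission overstates the difference by 0.09 to 1.70 and averaging recorded days understates it by 0.08 to 2.14. The largest is 2.14/16.64 = 13%.

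**5. Sensitivity to the table.** The printed enhanced Day 2 value (55) does not match the table's own conversion, 7 × 5 + 3 × 10 = 65, and the two must be reconciled. With 65, the planned difference is (557.5 − 431)/7 = 18.1 and the errors in step 3 become +0.82 and −0.81. The conclusion does not change.

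**6. Safety.** With 40 per arm, one unrecorded enhanced-arm event changes the risk difference by 1/40 = 2.5 points. As an assumed illustration, take 12/40 against 6/40, a difference of 15 points. Missing 1 event gives 11/40 − 6/40 = 12.5 points; missing 5 gives 7/40 − 6/40 = 2.5 points.

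**The case against.** The strongest reply is that the main route for intolerance already keeps the infant. The care team reduces nutrition under clinical routine (14.1, 24.1), and 13.1 retains those infants with their data. Parents are to be blinded (5.1), data before withdrawal are analysed in full, and adverse events during the trial go to the IRB and the safety committee (18.2). Ending collection at full withdrawal respects the parent's decision. All of this stands, and it limits how often the problem would arise. It does not recover data for an infant who is withdrawn.

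A reader might infer more than the documents support:

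- *That the rule breaks intent-to-treat and hides harm.* It can do some damage to both. Whether it does depends on withdrawals that the documents do not quantify.
- *That parents withdraw mainly because of intolerance.* No section says so. Blinding does not prevent withdrawal prompted by visible intolerance, but nothing shows this to be the typical case.
- *That any parental request to change nutrition counts as withdrawal.* Section 13.2 applies to withdrawal from the study. The protocol is silent on partial withdrawal and does not forbid it.
- *That a withdrawn enhanced infant would look like a control.* Setting 60.0 (enhanced, Days 1–3) beside 61.6 (control, Days 1–7) compares different days. The control mean for Days 1–3 is (26 + 40 + 55)/3 = 40.3.
- *That event rates would be roughly halved.* That needs withdrawal to be strongly concentrated in infants who later have the event. If withdrawal were unrelated to outcome and withdrawn infants left the denominator, the expected rate would be unchanged.

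The consent form is not among the documents reviewed and may already offer such options.

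**Conclusion.** The point holds as a weakness in the withdrawal rule. As written, 13.2 and 13.3 discard chart data that bear on the primary outcome and on safety, that could be kept with a parent's permission, and that 13.1 keeps when the attending makes the change.

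For the primary outcome the likely effect is modest: about 1 kcal/kg/day of 16.6 under the assumed 4 of 40 withdrawals after Day 3, and at most about 2.1 in the range examined. Only withdrawals within the first 7 days can affect it. The safety comparison is more fragile, because each missed enhanced-arm event is worth 2.5 points. Both results assume one-sided withdrawals, and the intake result also assumes a return to the control schedule. Imputation under missing at random would not repair a loss that is related to intolerance. The change is worth making because it is cheap and because data not collected may be unusable later without permission.

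**What to change.** Revise 13.2 and 13.3, and the consent form if it does not already say so, to separate three levels:

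1. **Study nutrition stopped only.** The infant stays in the trial and all measurements and visits continue, as 13.1 already provides after a change by the attending.
2. **Study procedures or visits stopped.** If the parent permits, chart abstraction of first-week intake, tolerance labs and morbidities continues to discharge.
3. **All further data use refused.** Collection stops; data already collected are analysed, as now.

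Record the level, date and reason, tabulate them by arm, and analyse infants at levels 1 and 2 in their assigned arm. This concerns data collection only and leaves clinical decisions as they are.

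The cost is a protocol and, if needed, consent wording amendment, one case-report field and a slightly longer withdrawal conversation. No new procedure or staff is needed, since the chart is already abstracted.

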### **14.0** Risks to Participants

14.1 Foreseeable Risks:

Intolerance of IV nutrition: Preterm infants often experience hyperglycemia, hypertriglyceridemia and cholestasis (elevated direct bilirubin) while on total parenteral nutrition in the first few weeks of life. It is possible that rates or severity of these problems may be increased in infants receiving higher amounts and/or faster advancement of macronutrients. Infant's glucose, triglyceride levels and direct bilirubin will be monitored per the clinical routine which is at least daily for the first week of life for glucose, twice weekly for triglycerides and at least weekly for bilirubin. More frequent checks will be initiated, again per clinical routine, should infants show any signs of intolerance. Hyperglycemia often requires treatment with insulin in very low birth weight preterm infants, and infants in the study will again be treated per the usual NICU protocol at the discretion of the care team. In addition, macronutrient provision will be decreased per clinical routine should infants show these sign of intolerance. Two recent small studies have found that earlier initiation and more rapid advancement of these macronutrients actually result in less hyperglycemia/insulin use, similar rates of hypertriglyceridemia and lower rates of parenteral nutrition associated cholestasis. Therefore, an important aspect of this exploratory research project is to assess whether early initiation and more rapid advancement will lead to increased provision of macronutrients or whether the nutrition will have to be scaled back due to intolerance and result in similar nutrient provision.

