In summary, recent neonatal literature continues to suggest the need for randomized trials of nutritional interventions that focus not only on weight gain, but more importantly on linear growth and FFM gains, and that can measure both neurodevelopmental and metabolic outcomes. Our expertise and experience in both neonatal body composition measurement AND methods of measuring early neurodevelopmental outcomes put us in an ideal position to trial an early enhanced nutrition intervention and potentially become a leader for future larger multi-center studies with long-term follow-up. This trial will not only allow us to determine the feasibility of providing additional nutrition to these sick infants, through close monitoring of metabolic tolerance (glucose, triglyceride and bilirubin levels) and careful detailed tracking of nutrient intake throughout their hospital stays, but will also provide us with preliminary data testing whether increasing all macronutrients incrementally shortly after birth eliminates early malnutrition, subsequent growth failure and neurodevelopmental delays.

- 2.2 Prelim Data: In our extensive prior work we have described differences in body composition between preterm and term infants, developed the first reference curves for preterm infant body composition, and shown relationships between early nutrition, illness and body composition trajectories through infancy among preterm infants. We were the first to describe associations between early FFM gains (not fat mass (FM) gains) and speed of processing and cognition. This observational work provides the necessary basis for our next phase of research aimed at increasing FFM gains prior to discharge and improving long-term growth, neurodevelopment and metabolic health for VLBW preterm infants through a randomized controlled nutritional intervention trial.

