### 4.0 Study Intervention

4.1 Description: This nutritional intervention is designed to accelerate the addition of macronutrients over the first week of life to minimize the period of malnutrition, and is based upon the findings of numerous smaller, less comprehensive studies and expert opinion. Once consent is obtained, and the infant is admitted to the NICU, enrolled infants will be randomized to either receive parenteral nutrition per the standard NICU parenteral nutrition protocol or via the enhanced nutrition protocol for the first week of life via random envelope selection. Stratified

block randomization will be performed. Infants will be stratified by gestational age (22-25, 26-29, 30-32 weeks). Within each stratum, permuted block randomization will ensure that study personal are unable to predict treatment allocation. Infants

randomized to the enhanced nutrition protocol will receive starter total parenteral nutrition (TPN) initiated at 80 mls/kg/day to provide protein at 4 grams/kg/day and a glucose infusion rate (GIR) of ~5.5 mgs/kg/min as soon as IV access has been obtained. Enhanced nutrition protocol infants will also be started on intralipids (IL) at 2 grams/kg/day once IV access is obtained. Infants randomized to the enhanced nutrition protocol will receive 4 grams/kg/day of protein throughout the first week of life. IL will be increased to 3 grams/kg/day on day of life (DOL) 2 and to 3.5 grams/kg/day on DOL 3. They will remain on this amount for at least the first week of life or until sufficient enteral feeding volumes have been established. GIR will be advanced by  $\sim 1.5 \text{ mgs/kg/min per day}$ throughout the first week of life to a maximum of 12-14 mgs/kg/min. Again, they will then remain on this amount until sufficient enteral feedings have been established (typically approximately 1-2 weeks). Infants randomized to the standard nutrition protocol will receive macronutrients per the caregivers discretion, most commonly initiated with starter TPN at 60 mls/kg/day giving 3 grams/kg/day of protein and a GIR of ~4 and IL provided at 0-1 gram/kg/day. Advancement is most typically by 1

mg/kg/min per day for GIR and 1 gram/kg/day per day for IL and protein in the standard NICU protocol. Pertinent aspects of the differences in nutritional treatment in intervention and control groups are summarized in the table below

	Day 1	Day 2	Day 3	Day 4	Day 5	Day 6	Day 7	
Control								
GIR	4.2	5	6	7	8	9	10	

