Nutritional Intervention: Once consent is obtained, and the infant is admitted to the NICU, enrolled infants will be randomized to either receive parenteral nutrition per the standard NICU parenteral nutrition protocol or via the enhanced nutrition protocol for the first week of life via random envelope selection. Infants randomized to the enhanced nutrition protocol will receive starter total parenteral nutrition (TPN) initiated at 80 mls/kg/day to provide protein at 4 grams/kg/day and a glucose infusion rate (GIR) of ~5.5 mgs/kg/min as soon as IV access has been obtained. Enhanced nutrition protocol infants will also be started on intralipids (IL) at 2 grams/kg/day once IV access is obtained. Infants randomized to the enhanced nutrition protocol will receive 4 grams/kg/day of protein throughout the first week of life. IL will be increased to 3 grams/kg/day on day of life (DOL) 2 and to 3.5 grams/kg/day on DOL 3. They will remain on this amount for at least the first week of life or until sufficient enteral feeding volumes have been established. GIR will be advanced by  $\sim 1.5$ mgs/kg/min per day throughout the first week of life to a maximum of 12 mgs/kg/min. Again, they will then remain on this amount until sufficient enteral feedings have been established (typically approximately 1-2

weeks). Infants randomized to the standard nutrition protocol will receive macronutrients per the caregivers discretion, most commonly initiated with starter TPN at 60 mls/kg/day giving 3 grams/kg/day of protein and a GIR of ~4 and IL provided at 0-1 gram/kg/day. Advancement is most typically by 1 mg/kg/min per day for GIR and 1 gram/kg/day per day for IL and protein in the standard NICU protocol.

Glucose, conjugated bilirubin and triglyceride levels will be monitored per standard NICU protocol and nutrition will be adjusted accordingly and insulin given per NICU protocol.

Nutritional intake will be recorded daily throughout the hopitalization, including kcal/kg/day and g/kg/day of protein by our NICU dietician. We will also gather data on days requiring TPN, type of feedings given (breast milk vs. formula) and degree of fortification (feeding additives). Following hospital discharge we will monitor intake through parent questionnaires monthly until the final (4 month CA) follow-up visit.

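### Section 13.1 would adjust the analysis for nutrition changes made after randomisation, which conflicts with intent-to-treat and could hide the scale-back the trial wants to measure

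*Combined protocol and SAP*

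**What the plan says.** Section 13.1 allows the attending neonatologist to change the study nutrition and continues: "These changes will not preclude continuing in the study, but rather will be adjusted for when analyzing the study data". It gives no method and excepts no outcome. Section 14.1 says macronutrients will be reduced when infants show intolerance, and section 24.1 says the care team may change provision when such signs appear.

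The analysis plan (item 15.1 under section 16.0) is to be carried out "using an intent-to-treat approach, with a 2tailed p<0.05 as the threshold for statistical significance". Its primary models for body composition, ERP and IGF-1 test assigned group. Covariates such as gestational age and degree of illness go into secondary models. No model is given for first-week intake, although the primary outcome in section 3.1 is to "determine if infants randomized to the enhanced nutrition protocol receive higher amounts of calories and protein throughout the first week of hospitalization".

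Two passages show what feasibility is meant to cover. Section 14.1 asks whether provision will rise or "whether the nutrition will have to be scaled back due to intolerance and result in similar nutrient provision". Section 2.1 says feasibility will be determined "through close monitoring of metabolic tolerance (glucose, triglyceride and bilirubin levels) and careful detailed tracking of nutrient intake throughout their hospital stays".

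**The concern.** A cut in glucose, lipid or protein because an infant did not tolerate the enhanced regimen is something the assigned treatment can cause. Conditioning on it no longer compares the groups as randomised. For intake the problem is sharper, because the cut is part of the result. Adjusting for it estimates what intake would have been without a cut, whereas the trial asks what was delivered.

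The control arm makes the adjustment harder to define. "Infants randomized to the standard nutrition protocol will receive macronutrients per the caregivers discretion", so there is no fixed schedule from which a control infant's change could be counted. A change flag may therefore fall mostly on the enhanced arm, which is where it distorts most.

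At stake is the primary objective. The pilot is meant to lead to a larger trial, and an adjusted intake result could make the enhanced protocol look fully deliverable when many infants had been scaled back.

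**Working it through.** **1. Planned gap (table in section 4.1).** Control: 26 + 40 + 55 + 70 + 75 + 80 + 85 = 431 kcal/kg. Enhanced: 47.5 + 55 + 77.5 + 85 + 92.5 + 95 + 95 = 547.5. Both match the printed totals. The planned gap is D = (547.5 − 431)/7 = 116.5/7 = 16.64 kcal/kg/day.

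**2. Model examined.** The plan states none, so I take the plain reading as an assumption: weekly-mean intake regressed on arm and a change flag. Let p_E and p_C be the shares flagged in the enhanced and control arms, and b the pooled within-arm slope on the flag. Then

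adjusted gap = delivered gap − b × (p_E − p_C).

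**3. No control flagged; a share s of the enhanced arm cut to control level all week.** Delivered gap = D(1 − s). The slope comes only from the enhanced arm, b = −D, so adjusted gap = D(1 − s) + D·s = D.

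| s | Delivered | Adjusted |
|---|---|---|
| 10% | 15.0 | 16.6 |
| 25% | 12.5 | 16.6 |
| 50% | 8.3 | 16.6 |
| 75% | 4.2 | 16.6 |

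Simulation with 40 per arm and an assumed SD of 10 gave adjusted means of 16.57 to 16.67 across these rows. If every enhanced infant and no control were flagged, arm and flag would be collinear and the arm effect could not be estimated.

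**4. Half the enhanced arm cut to control level; 25% of controls flagged with a drop of D/2.**
- Delivered: (D − 0.5D) − (−0.25 × 0.5D) = 0.625D = 10.4.
- Slope, weighted by within-arm flag variance (0.5 × 0.5 = 0.25 and 0.25 × 0.75 = 0.1875): b = −(0.25 × 1 + 0.1875 × 0.5)D/0.4375 = −0.786D.
- Adjusted: 0.625D + 0.786D × (0.50 − 0.25) = 0.821D = 13.7.

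**5. Equal flagging.** If p_E = p_C, the correction term is zero and the adjusted gap equals the delivered gap.

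**6. Sensitivity to the table.** The Day 2 enhanced entry is printed as 55, but the table's own conversion gives 7 × 5 + 3 × 10 = 65. With 65, D = 126.5/7 = 18.1, and halving it gives 9.0. The ratios above do not change.

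**7. Precision of a tolerance table.** With an assumed rate of 20% in each arm of 40, the 95% half-width is 1.96 × √(2 × 0.2 × 0.8/40) = 0.175, about 18 points. Newcombe intervals are −17.6 to 17.6 points for 8/40 v 8/40, and −0.1 to 38.1 for 16/40 v 8/40.

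**The case against.** The strongest reply is that the sentence sits under withdrawal, names no model, and should be read with section 16.0, which states intent-to-treat, tests assigned group in the primary models and keeps covariates for secondary ones. Adjusting intake for a change in intake would also be an odd thing to do. This stands in part: the documents do not show that the primary comparison will be adjusted. But section 13.1 is a positive instruction without exceptions, and section 16.0 gives no intake model that would override it.

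A second reply is that the 8.3 v 16.6 contrast depends on no control being flagged, while the reduction rule in section 14.1 is not limited to one arm. That is correct, and it is why steps 4 and 5 show the distortion shrinking and then vanishing.

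A reader might go further and infer that the plan leaves tolerance unassessed, or that an intake outcome cannot answer section 14.1. The documents do not support this:
- Both alternatives in the section 14.1 sentence are intake results, which the section 3.1 outcome addresses.
- "Nutritional intake will be recorded daily throughout the hopitalization, including kcal/kg/day and g/kg/day of protein by our NICU dietician", so a mid-week cut would be visible day by day. Masking by a weekly total would need a weekly summary that the plan never specifies.
- Section 14.1 says "Hyperglycemia often requires treatment with insulin in very low birth weight preterm infants", but it and section 5.2 present insulin and reduced provision together. Treatment by insulin alone, with intake untouched, is not described.
- Blood results are in the dataset (section 6.2), and the DSMC reviews the tolerance labs, blinded, at its interim look (section 18.2).

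**Conclusion.** The conflict between section 13.1 and the intent-to-treat statement is real and should be resolved before analysis. Its size is conditional. If the adjustment were applied to intake as a covariate, the estimate would move from the delivered gap towards the planned 16.6 kcal/kg/day: from 8.3 to 16.6 with half the enhanced arm cut all week and no controls flagged, from 10.4 to 13.7 with 25% of controls flagged at half-size drops, and not at all with equal flagging. The shares cut and flagged are assumptions, since the documents give no rates. Section 13.1 also covers any discretionary change; the link to intolerance comes from sections 14.1 and 24.1.

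The missing final by-arm tolerance summary is a lesser, reporting point. It rests on section 2.1, which names tolerance as a route to judging feasibility. Nothing here implies that the enhanced protocol is tolerated worse: section 14.1 calls increased problems possible and cites small studies with similar or lower rates.

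**What to change.** Amend section 13.1 to say three things:
- All primary comparisons, including first-week calories and protein, are by assigned group without adjustment for nutrition changes.
- Nutrition changes are reported by arm as outcomes.
- Any analysis that adjusts for them is labelled secondary or sensitivity.

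Repeat the first statement in the analysis plan, where intake currently has no model.

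Add one descriptive table by arm, set beside daily calorie and protein intake, with 95% confidence intervals for the differences. It should cover glucose, triglyceride and bilirubin results, insulin use, and reductions made for intolerance. Any thresholds should be written down beforehand. Because section 14.1 calls for more frequent checks once intolerance appears, show the number of tests per infant as well.

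The cost is a few sentences and one table, with no extra blood tests. Insulin use and the reason for each change are not named among the data items, so they may have to be abstracted from the medical record. The downside is precision: at about ±18 points with 20% in each arm, the table describes tolerance and cannot show that it is equal.
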